Subjects, their parents, investigators, staff, and persons performing the assessments will remain blind to treatment assignment from the time of randomization until their completion of the study after 12 weeks. Randomization data are kept strictly confidential until the time of unblinding and are accessible only to authorized persons. The identity of the treatments will be concealed by the use of study drugs that are identical in packaging, labeling, schedule of administration and appearance. Placebo and study drug will be prepared in a like fashion at the Yale-New Haven Hospital Investigational Drug Service pharmacy.

NAC is an altered form of the amino acid cysteine, which is commonly found in food and synthesized by the body. N-acetylcysteine (NAC) is generally well tolerated and has been extensively used in the treatment of acetaminophen overdose/toxicity at high doses for many years. The dosage in acute acetaminophen overdose is a 140mg/kg loading dose, followed by a maintenance dose of 70mg/kg administered every 4 hours for 17 consecutive doses. The dose used to treat acetaminophen overdose in children is approximately 10-fold greater than the maximum dose we will use in this study. Although generally well-tolerated, the PDR indicates that adverse reactions reported with oral NAC include nausea, vomiting, diarrhea, headache (especially when used along with nitrates) and rashes when used at higher doses (Cheng, Lin et al. 2007). There are rare reports of renal stone formation and cases of bronchospasm with intravenous use only. The long-term use of NAC has been well-studied in the treatment of Chronic Obstructive Pulmonary Disease and was extremely well-tolerated (Grandjean, Berthet et al. 2000). NAC has been well-tolerated in the treatment of adults with OCD and trichotillomania (TTM) at a maximum dose of 3000mg (Pittenger, Krystal et al. 2005; Lafleur, Pittenger et al. 2006).

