The table below indicates the clinical ratings scheduled planned for the trial. If subjects' have significant ADHD, tic, anxiety or depression symptoms at screening, ratings of these symptoms will be followed regularly at study assessments. Subjects will be encouraged to continue outside therapy and will be required to continue all concurrent medications during the course of this trial. Subjects will also be asked about the number of missed doses of medications at each study visit.

Measure	Screening/ Baseline	Week 2	Week 4	Week 8	Week 12
CY-BOCS	X	X	X	X	X
DY-BOCS	X	X	X	X	X
YGTSS	X		X	X	X
ADHD-RS	X		X	X	X
CDI	X		X	X	X
MASC	X		X	X	X
MGH-HPS	X		X	X	X
CGI	X	X	X	X	X
PAERS	X	X	X	X	X
NAC dose	600mg BID	1200 mg BID	1200 mg BID	1200 mg BID	1200 mg BID

3. **Statistical Considerations:** Describe the statistical analyses that support the study design.

We will use the CY-BOCS as our primary outcome measure. Our primary analysis will involve a mixed effects model using weekly CY-BOCS ratings from baseline to 12 weeks with treatment (NAC/placebo) as a fixed factor and time as a within-subject factor. We will adhere to intention-to-treat principles in our analysis. We powered our study to have 80% power to detect a large effect of NAC ($d=0.9$) assuming $\alpha=0.05$. Given a similar variance in the Cy-BOCS scores in previous placebo-controlled trials of pediatric OCD, we would expect this effect size to correspond to a 6.5 point difference in Cy-BOCS between the NAC and placebo groups (POTS

HIC#1004006623

2004). By comparison, the effect size of NAC in the treatment of adults with trichotillomania, using the MGH-HS ($d=1.2$, $N=50$), and in bipolar depression, using the Montgomery-Asberg Depression Rating Scale (MADRS) ($d=0.8$, $N=80$) was considerably larger (Grant, Odlaug et al. 2008).

As a secondary outcome we will examine the safety and tolerability of NAC. Given our sample size of 40 we will have limited power to detect adverse events of low frequency. That being said, assuming that we do not see a side-effect in the placebo group, we will have 80% power to detect NAC related side-effect, if it occurs in one-third of NAC treated subjects. Frequency of side-effects will be measured with the PAERS as discussed in the assessments section.

SECTION VI: RESEARCH INVOLVING DRUGS, DEVICES, BIOLOGICS & PLACEBOS

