There is no significant evidence that the rate of response to switching to a serotonin norepinephrine reuptake inhibitor (SNRI) such as venlafaxine or clomipramine is any different. SSRIs are associated with side effects such as insomnia, sedation, nausea, diarrhea, sexual dysfunction, behavioral activation and suicidal ideation.

3. Continuing current therapies – current evidence suggests that the treatment response to SSRIs or CBT plateaus by 3 months after the initiation of treatment. The risk of continuing their current therapy varies based on the nature of that therapy, but does not contain the additional risks associated with NAC.

(b) 12 weeks.

Since the study medication is added to the children's current medications, the risk of symptoms worsening is not significantly greater in this clinical trial than it would be if the patient's medications were changed as part of standard clinical care. The only additional risks in this study are potential adverse effects of N-acetylcysteine or no response in the placebo group. We will monitor subjects carefully for these changes during the course of the study and discontinue the study and provide or refer subjects for appropriate treatment as necessary. Subjects assigned to placebo will have the opportunity to receive active NAC after the 12 weeks.

(c) If a child is discontinued from the study because of the worsening of symptoms, the child, if receiving active medication, will be referred for appropriate behavioral and pharmacological treatment, and if on placebo will be offered active medication in addition to the above therapy.

6. Use of Controlled Substances:

Will this research project involve the use of controlled substances in human subjects?

Yes No See instructions to view controlled substance listings.

7. Continuation of Drug Therapy After Study Closure Not applicable to this project

Are subjects provided the opportunity to continue to receive the study drug(s) after the study has ended? Yes No

If yes, describe the conditions under which continued access to study drug(s) may apply as well as conditions for termination of such access.

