Subjects receiving placebo will receive NAC free of charge for the next 12 weeks of the protocol. They will continue clinical sessions as needed for the next 12 weeks. After receiving 12 weeks of NAC, they will be instructed on how to obtain NAC over-the-counter but encouraged to receive continued psychiatric care. We will make appropriate clinical referrals as necessary at the end of the trial. We will offer continued consultations to outside practitioners throughout the study period.

SECTION VII: HUMAN SUBJECTS

1. **Recruitment Procedures:** How will potential subjects be identified, contacted and recruited?
Attach copies of any recruitment materials that will be used.

Flyers
 Posters
 Letter

Internet/Web Postings
 Mass E-mail Solicitation
 Departmental/Center Website

Radio
 Telephone
 Television

version

Page 14 of 27

HIC#1004006623

- Medical Record Review Departmental/Center Research Boards Newspaper
 Departmental/Center Newsletters Web-Based Clinical Trial Registries
 Other (describe): Clinicaltrials.gov Registry (do not send materials to HIC)

1. a. **Assessment of Current Health Provider Relationship for HIPAA Consideration:**

Does the Investigator or any member of the research team have a direct existing clinical relationship with any potential subject?

- Yes, all subjects
 Yes, some of the subjects
 No

If yes, describe the nature of this relationship.

We may recruit subjects who come to be seen at our clinic. Some children may be referred for psychopharmacology consult. Other subjects may come specifically because of interest in the study. No subjects will be taken off current medication or withdrawn from ongoing therapy in order to participate in the trial, unless the current medication is ineffective or causing unacceptable adverse effects. Families of children who are not interested in the study will be treated in the usual clinical manner.

2. **Subject Population** Provide a detailed description of the targeted involvement of human subjects for this research project.

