5. **Potential Benefits:** Identify any benefits that may be reasonably expected to result from the research, either to the subject(s) or to society at large. (Payment of subjects is not considered a benefit in this context of the risk benefit assessment.)

Children may benefit from the thorough medical and psychiatric evaluations that they will receive while participating in the study. During the study, subjects will also receive a higher level of evaluation and care than routine treatment. Additionally, subjects may benefit from the study medication.

SECTION X: RESEARCH ALTERNATIVES AND ECONOMIC CONSIDERATIONS

1. **Alternatives:** What other alternatives are available to the study subjects outside of the research?
 - 1) Continuing patient's current medications or therapy, which might include various SSRIs or clomipramine) or cognitive behavioral therapy. Both these interventions have demonstrated efficacy for the treatment of pediatric OCD. All subjects will be recommended to engage in adequate trials of both these interventions before enrolling in the trial.
 - 2) Antipsychotics in addition to SSRIs have shown some benefit for the treatment of refractory OCD in adults. These medications are associated with a significantly greater side effect burden than NAC. Families will be made aware of this additional treatment option prior to enrolling in this study.
 - 3) Since N-Acetylcysteine is FDA approved for use to reduce the extent of liver injury after acetaminophen overdose, the patient's doctor might feel comfortable prescribing it off label to the patient.
2. **Payments for Participation (Economic Considerations):** Describe any payments that will be made to subjects and the conditions for receiving this compensation.
Subjects will be paid a total of \$150 for participation in the study -- \$50 screening assessment, \$25 for each of the 4 follow-up visits. .
3. **Costs for Participation (Economic Considerations):** Clearly describe the subject's costs associated with participation in the research, and the interventions or procedures of the study that will be provided at no cost to subjects.
Families will not be charged for the study medications, clinical assessments, services or laboratory tests directly related to the study. As noted above, some subjects may be seen for a clinical consultation prior to study entry. This clinical consultation will be charged as part of standard of care in the usual manner.

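### No early-termination CY-BOCS is scheduled, so a child discontinued for worsening between visits leaves the primary model without the score that led to removal

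*Combined protocol and SAP*

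**What the plan says.** **Care after discontinuation.** Section VI, 5. Use of Placebo, item (c) opens with its trigger: "If a child is discontinued from the study because of the worsening of symptoms". The child then, "if receiving active medication, will be referred for appropriate behavioral and pharmacological treatment, and if on placebo will be offered active medication" on top of the same referral. The paragraph before item (c) sets no fixed time for such a decision: "We will monitor subjects carefully for these changes during the course of the study and discontinue the study".

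**Blinding.** Under Section V, 3. Research Plan, children, parents, investigators, staff and assessors "will remain blind to treatment assignment from the time of randomization until their completion of the study after 12 weeks". The protocol adds: "Randomization data are kept strictly confidential until the time of unblinding and are accessible only to authorized persons". No early route to the code is described.

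**Ratings.** The schedule table in the same section lists the CY-BOCS at screening/baseline and at weeks 2, 4, 8 and 12, with no early-termination column. The Statistical Considerations name the CY-BOCS as primary outcome and plan a "mixed effects model using weekly CY-BOCS ratings from baseline to 12 weeks", under intention-to-treat principles. Section X, 2. Payments for Participation pays $25 "for each of the 4 follow-up visits".

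**After the study.** For placebo children who go on to NAC, Section VI, 7 provides clinical care, not ratings: "They will continue clinical sessions as needed for the next 12 weeks".

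**The concern.** Discontinuation for worsening is an event closely tied to the primary outcome. When it happens, the plan does something that reveals the arm, and it asks for no CY-BOCS first. If the child leaves between scheduled visits, the score that explains the departure is never recorded. The child enters the analysis with a last rating taken before the worsening.

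A likelihood-based mixed model copes well with dropout when the scores already in the data explain it. It copes less well when dropout depends on a score that nobody wrote down. If removals for worsening were more common in one arm, the estimated NAC-placebo difference would rest partly on children who look better in the data than they were when they left. Once the arm is known, a sound rating of that moment can no longer be obtained blind.

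**Working it through.** **1. The plan's own figure.** Inputs: d = 0.9, 80% power and alpha 0.05 (Statistical Considerations), 1:1 allocation (Research Plan), about 40 children (Targeted Enrollment). The test is assumed two-sided. Per arm, n = 2(1.960 + 0.842)² / 0.9² = 2 × 7.851 / 0.81 = 19.4, rounded up to 20, so 40 in total. The figure reproduces. This point does not change it.

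**2. Does the care rule reveal the arm?** Under item (c) a NAC child gets a referral, and a placebo child gets the referral plus an offer of NAC. Staff cannot apply the rule without the assignment, and the family can read it from what is or is not offered. Item (c) gives no date. The offer is made together with the referral, so discontinuation is the natural time. The chance for placebo children to take NAC after 12 weeks is already given in the paragraph before.

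**3. Is any CY-BOCS tied to that event?**
- Schedule table: baseline and weeks 2, 4, 8 and 12 only.
- Payments: $50 for screening + 4 × $25 = $150, which is the stated total. No discontinuation visit is counted.
- Post-study NAC for placebo children: clinical sessions only.
- Statistical Considerations: intention to treat is promised, but no rating or handling of discontinued children is described.

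The answer is no.

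**4. How old can the last rating be?** Age = time of leaving − time of the last scheduled rating.

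| Child leaves between | Last CY-BOCS | Age of that rating |
|---|---|---|
| baseline and week 2 | baseline | up to 2 weeks |
| weeks 2 and 4 | week 2 | up to 2 weeks |
| weeks 4 and 8 | week 4 | up to 4 weeks |
| weeks 8 and 12 | week 8 | up to 4 weeks |

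For example, a child who worsens and leaves at week 7 has a last rating 7 − 4 = 3 weeks old and contributes nothing after week 4.

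The analysis text speaks of weekly ratings. If ratings were truly weekly, the gap would be at most 1 week. The table and the four paid follow-up visits both point to the longer gaps.

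**5. Worsening found at a scheduled visit.** A CY-BOCS is due that day, so the score may well be captured. The plan does not say that it must be completed before the arm-dependent offer.

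**6. What cannot be calculated.** The documents give no rate of discontinuation for worsening, no split by arm and no size of worsening. The effect on the mixed-model estimate therefore cannot be derived from them.

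**The case against.** The case against is substantial, and much of it stands.

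- *Blinded ratings do come before disclosure.* Every scheduled CY-BOCS is made by an assessor meant to be blind. A reader might infer from item (c) that no blinded rating precedes disclosure, or that the blind fails for the trial as a whole. The text supports neither. What is missing is a rating tied to early discontinuation.
- *Worsening may be picked up at a visit.* Adverse events are assessed at each visit (Section IX, 3), dose-increase decisions are made at visits (Section IX, 2), and unscheduled visits are not described. This narrows the gap to departures between visits, plus the unstated order of rating and offer at a visit.
- *The date of the offer is inferred.* This is true. If the sponsor meant NAC to be offered only after week 12, early disclosure would not arise. The score at departure would still be unrecorded.
- *Unblinded rating is hypothetical.* A reader might infer that these children will be rated by someone who knows the arm. The plan schedules no rating after discontinuation, so this would happen only if extra ratings were collected.
- *The section answers an ethics form.* Silence there on code-break steps is weak evidence by itself. The missing column in the rating schedule does not depend on it.

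**Conclusion.** The point holds in a limited form. The protocol has no CY-BOCS at early termination. A child discontinued for worsening between visits leaves a last score up to 2 weeks old before week 4 or up to 4 weeks old after it, and the worsening is missing from the primary mixed model. At a scheduled visit, the order of rating and offer is left open. This rests on reading the schedule table, not the word "weekly", as the true rating plan. The part about disclosure also assumes that the offer is made at discontinuation.

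No size is attached. A reader might size it by removing children from a week-12 t-test: with 1 to 4 of 20 lost in each arm, power would go from 79% to 77%, 75%, 72% or 69%. Those figures describe dropout in general. The planned mixed model keeps the ratings already made, the numbers lost are assumed, and a rating at departure would not restore a week-12 value. An unrecorded worsening of an assumed number of points, averaged over 20 children, is likewise not the bias of a mixed model, which projects unobserved values from the observed data.

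The number of children concerned may be small or zero. The change is worth considering because it is cheap and removes a source of outcome-related missing data.

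**What to change.** In the Section V schedule table and in Section VI, 5, item (c):

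- Add an early-termination CY-BOCS for any child discontinued for worsening, in both arms. The existing blinded rater completes it before the assignment is disclosed or NAC is offered. At a scheduled visit, that visit's CY-BOCS serves, provided it is done first.
- State that urgent care does not wait for the rating. The care promised in item (c) is unchanged.
- State when the NAC offer is made, and that anyone who learns a child's assignment does not rate that child again.

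In the Statistical Considerations, include this rating in the primary mixed model. If time is continuous, use the actual time. If time is categorical, assign the rating to the nearest scheduled visit by a window fixed in advance, and say which rating counts if that visit already has one.

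The cost is one unscheduled CY-BOCS per discontinued child, a blinded rater available for it, and a few sentences of text. No new instrument is needed, no scheduled rating is removed, and the sample size stays at 40.

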Assessment: *Pre-study screening procedure:* After an initial phone screen to rule out obvious exclusions from the study protocol, potential subjects will have an initial evaluation that will be performed by a multidisciplinary clinical team. Exclusions in screening would include (1) Comorbid bipolar disorder, psychotic disorder, substance use disorder, developmental disorder or mental retardation (IQ<70), (2) asthma diagnosis requiring treatment in the last 3 months, and (3) a change in psychotropic medications or behavioral treatment for OCD within the last month. In addition to a standard clinical evaluation consisting of history, and mental status exams, subjects will receive a clinical diagnostic interview using the Kiddie-Schedule for Affective Disorders and Schizophrenia (K-SADS) (Kaufman, Birmaher et al. 1997). Additional baseline ratings will be conducted for OCD, tic, depression and anxiety severity using: 1) Children's Yale-Brown Obsessive-Compulsive Scale (CY-BOCS) (Scahill, Riddle et al. 1997), (2) Dimensional Yale-Brown Obsessive-Compulsive Scale (DY-BOCS). Additional baseline ratings

HIC#1004006623

will be conducted for OCD, tics, trichotillomania, depression and anxiety severity using (3) Yale Global Tic Severity Scale (YGTSS) (Leckman, Riddle et al. 1989), (4) ADHD Rating Scale (ADHD-RS) (DuPaul, Power et al. 1998), (5) Multidimensional Anxiety Scale for Children (MASC) (March, Parker et al. 1997), (6) Children's Depression Inventory (CDI) (Kovacs 1985), (7) Massachusetts General Hospital – Hairpulling Scale (MGH-HPS) (Keuthen, O'Sullivan et al. 1995), (8) Clinical Global Impression (CGI) scale (Guy 1976) and (9) Pediatric-Adverse Events Rating Scale (PAERS) (March, Karayal et al. 2007). The pediatric adverse events rating scale will be used to monitor safety throughout the trial. A medical assessment including vital signs, physical exam and urine drug screen and pregnancy test will be completed prior to study enrollment. The measures utilized in this study are outlined below.

Baseline Assessments	Medical Assessments	Rating scales
K-SADS	Vital Signs	CY-BOCS DY-BOCS
Psychiatric History	Physical Exam	YGTSS ADHD-RS
General Medical History	Mental Status Exam	CDI MASC
	Urine Toxicology	MGH-HPS CGI
	Urine Pregnancy Test	PAERS

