NAC will be stored at the YNHHS IDS pharmacy. Placebo will be placed in the same capsules as NAC, thus NAC and placebo will look and smell identical.

5. **Use of Placebo:** **Not applicable to this research project**

Provide a justification which addresses the following:

- a. Describe the safety and efficacy of other available therapies (if any).
- b. State the maximum total length of time a participant may receive placebo while on the study.
- c. Address the greatest potential harm that may come to a participant as a result of not receiving effective therapy (immediate or delayed onset.)
- d. Describe the procedures that are in place to safeguard participants receiving placebo.
 - (a) Pharmacotherapy with SSRIs and cognitive behavioral therapy are both relatively safe and effective treatments for pediatric OCD (POTS 2004). We will recommend to all subjects considering enrollment in this trial that they engage in adequate trials (>3 months) of each of these interventions prior to enrolling in this trial. Assuming a child has significant residual OCD symptoms despite engaging in both these treatments, additional options include (1) antipsychotic augmentation, (2) switching SSRIs and (3) continuing on their current treatments.
 1. Antipsychotic Augmentation – Randomized, placebo-controlled studies in adults with OCD indicate that antipsychotic addition to ongoing SSRI monotherapy is a modestly effective treatment for refractory OCD. Estimates indicate that the Number needed to treat for this intervention is 5 with an outcome measure of treatment response. However, antipsychotic treatment is associated with significant side-effects including sedation, weight-gain, metabolic side effects such as diabetes and lipid abnormalities and the risk of extrapyramidal side effects such as tardive dyskinesia and akathisia. The risk of these side effects appears more pronounced in children than adults and no controlled studies for OCD have been conducted in these medications.
 2. For children who have tried only 1 SSRI an additional option is to switch to a different SSRI or SNRIs such as venlafaxine and clomipramine. There are no controlled studies assessing efficacy of medication switches in children with OCD. Data in adults suggest that if a patient has not responded to 1 SSRI the likelihood of responding to a different one is 25% and if they have not responded to 2 SSRIs, the likelihood of responding to a third is 10%.

HIC#1004006623

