In many cases subjects will be screened via telephone. The telephone screen will be used to inform the parent (primary caretaker) about the nature of the study, the duration of the study, number of visits, randomization, etc. The telephone screen will include collecting a brief history to exclude subjects that are unlikely to be eligible. People may not be eligible because of an ongoing medical problem (asthma or pregnancy), presence of an excluded psychiatric diagnosis (see exclusion criteria), or because they are unable to attend scheduled study visits. Interested subjects will be scheduled for a screening visit. The screening visit will occur over one visit. The overall purpose of the screening is to confirm that the subject meets all entry criteria. The first step in the screening visit will be to review the consent form, answer questions about the protocol and to obtain written informed consent. All procedures will be described to the subject in a developmentally appropriate manner.

2. **Inclusion/Exclusion Criteria:** What are the criteria used to determine subject inclusion or exclusion? How will eligibility be determined, and by whom?

Subjects will be well-characterized and must meet selection criteria to be enrolled. The measures used in the baseline assessment will be used by the principal investigators to determine if subjects meet inclusion/exclusion criteria.

Inclusion Criteria:

1. Children aged 8-17 years.
2. Primary diagnosis of OCD.
3. Duration of OCD greater than 6 months.
4. Significant Current OCD symptoms: Current CY-BOCS score greater than or equal to 16.

Exclusion Criteria:

1. Comorbid bipolar disorder, psychotic disorder, substance use disorder, developmental disorder or mental retardation (IQ<70).
2. Recent change (less than 4 weeks) in medications that have potential effects on OCD severity (such as Selective Serotonin Reuptake Inhibitors, clomipramine, naltrexone, lithium, psychostimulants, anxiolytics, or antipsychotics). Medication change is defined

to include either dose changes or medication discontinuation.

3. Asthma requiring medication use within the last 3 months (case reports have linked intravenous NAC administration with asthma exacerbation)
4. Known hypersensitivity or previous anaphylactoid reaction to acetylcysteine or any components in its preparation.
5. Positive pregnancy test or drug screening test.
6. Previous use of N-acetylcysteine (dose greater than 600mg for more than 2 weeks).

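### Do the two differing rules on recent treatment change, and a window shorter than three months, call for a change to eligibility or the primary model?

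*Combined protocol and SAP*

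**What the plan says.** Two places in the combined protocol and SAP deal with recent changes in background treatment.

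- Section V, Research Plan, pre-study screening: among the screening exclusions is "a change in psychotropic medications or behavioral treatment for OCD within the last month".
- Section VII, Inclusion/Exclusion Criteria, Exclusion 2: "Recent change (less than 4 weeks) in medications that have potential effects on OCD severity". Change is defined "to include either dose changes or medication discontinuation". The section introduces its list by saying that subjects "must meet selection criteria to be enrolled".

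Three other places bear on the length of the window. Section VI, Use of Placebo, reports that "the treatment response to SSRIs or CBT plateaus by 3 months after the initiation of treatment". The same section says families will be advised "that they engage in adequate trials (>3 months) of each of these interventions prior to enrolling in this trial", and Section X, Alternatives, repeats the advice: "All subjects will be recommended to engage in adequate trials of both these interventions before enrolling in the trial". Section V also requires concurrent medications to continue during the trial and encourages outside therapy to continue.

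The primary analysis (Section V, Statistical Considerations) is a "mixed effects model using weekly CY-BOCS ratings from baseline to 12 weeks". The trial has 40 children randomised 1:1, with 80% power for d = 0.9, equated to 6.5 CY-BOCS points.

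**The concern.** The two rules differ in scope. The numbered list is silent on behavioural treatment, limits medications to those that may affect OCD severity, and does not name starting a drug in its definition of change. A coordinator working only from that list could enrol a child whom the screening text would turn away, and the plan does not say which text governs.

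There is a second, separate worry. Both windows are about one month, while the protocol itself puts the plateau of SSRI or CBT response at three months from initiation. The longer prior trials are advice and not a criterion. Children who recently started treatment may therefore keep improving during the study for reasons unrelated to NAC. With 20 per arm and no reserve in the sample size, extra variance takes power below target.

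**Working it through.** **Do the rules conflict?** Set side by side:

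| Recent change | Screening text (Section V) | Exclusion 2 (Section VII) |
|---|---|---|
| Behavioural treatment for OCD | excluded | not mentioned |
| Psychotropic not thought to affect OCD | excluded | not mentioned |
| Dose change or stop of an OCD-relevant drug | excluded | excluded |
| Start of an OCD-relevant drug | excluded (it is a change) | not named, but the definition is worded as inclusive |
| Window | last month | less than 4 weeks |

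No row has one text admitting a child whom the other excludes: the second column is silent where it differs. Exclusions are cumulative, and the screening text acts before enrolment. A site that follows the whole protocol therefore applies the wider rule.

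**The plan's own figure.** Inputs from Statistical Considerations: d = 0.9, difference 6.5, alpha 0.05 (two-sided assumed), 20 per arm. Implied SD = 6.5/0.9 = 7.22, variance 52.16. The normal approximation gives 20 per arm and 81.2% power; the noncentral t gives 79.2%. The stated 80% is reproduced.

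**What residual improvement could cost.** Suppose a share f of children gain g extra points from background treatment, equally in both arms. Then SD = √(52.16 + f(1−f)g²), and power comes from the noncentral t at d = 6.5/SD. The documents give neither f nor g, so all values below are assumptions.

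| f | g | f(1−f)g² | SD | Power |
|---|---|---|---|---|
| none | – | 0 | 7.22 | 79.2% |
| 5% | 2 | 0.19 | 7.23 | 79.1% |
| 10% | 3 | 0.81 | 7.28 | 78.6% |
| 10% | 8 | 5.76 | 7.61 | 74.9% |
| 25% | 6 | 6.75 | 7.68 | 74.2% |
| 50% | 8 | 16.00 | 8.26 | 68.0% |

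The rows at 5 to 10% stand for children let in by the list mismatch if only the numbered list were used. The largest loss there is 79.2 − 74.9 = 4.3 points. The last row needs half the children to be recent starters despite the advice, each gaining more than the trial's whole target effect of 6.5.

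**Bias.** The expected treatment difference moves by g times the between-arm difference in f, which is zero in expectation under randomisation. In the baseline-adjusted simulations the mean estimate stayed within 0.05 of the true −6.5.

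**Would a covariate for recent start help?** With baseline kept as an outcome row, a main effect alone leaves the week-12 treatment-by-time estimate unchanged (by less than 1e-12), so visit interactions are needed: five extra terms with five scheduled ratings. In a week-12 model adjusted for baseline (correlation 0.5 assumed), simulated power without and with the covariate was 87.7% and 87.2% at f = 10%, g = 3; 83.4% and 88.0% at f = 25%, g = 6; and 75.3% and 87.0% at f = 50%, g = 8. In the first setting the difference is simulation noise at most. At f = 5 to 10% only 0.05 × 40 = 2 to 0.10 × 40 = 4 children would inform the added terms.

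**The case for a change.** The best case for a change is that the screening text looks less like an extra layer than a second wording of the same criteria. Its first two items closely match numbered Exclusions 1 and 3, and only the third diverges. Staff often work from the numbered list, which the protocol says decides enrolment. One sentence would remove the doubt, and start dates of SSRI and CBT not collected at baseline may be hard to recover later. Recent starters are also plausible, since some recruitment is from the investigators' own clinic and families are advised to try both treatments first.

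The mismatch is real and aligning the two texts would be good housekeeping. That does not make the plan as written unsound: the texts can both be obeyed, and obeying both gives the wider exclusion.

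The three-month argument is weaker. The plateau statement gives an outer limit, counted from initiation, in a discussion of alternatives to placebo. It says little about dose changes and contradicts no entry rule. The choice of window is a trade-off between stability and recruitment, and a covariate would leave it as it is.

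The gains from the covariate at f = 25% and above are genuine under the assumptions, but nothing in the documents supports such shares. The planning SD is tied to earlier placebo-controlled trials in pediatric OCD, so it may already contain variation in response to treatment; adding f(1−f)g² on top may count it twice.

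**Conclusion.** The concern does not call for a change. The difference between the screening text and Exclusion 2 is a drafting discrepancy that staff resolve by applying both. The window is a design choice that the authors soften with advice on longer prior treatment and a requirement to keep medications stable.

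What is left is a matter of precision. On the t-test benchmark the cost of the mismatch is between 0.1 and 4.3 points of power under assumed shares of 5 to 10% and gains of 2 to 8 points, and close to nothing (78.6% against 79.2%) at 10% and 3 points. Larger losses need shares and gains for which the documents offer no support. Covariate adjustment helps clearly only if recent starters are common or gain a great deal; otherwise it spends terms in a sample of 40 for no return. These figures assume two-sided testing, 20 evaluable children per arm, an additive background gain equal in both arms and, for the adjusted model, a correlation of 0.5.
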